## **6. ANALYSIS INTERPRETATION**

Multiple objectives and endpoints require type I error control. Full alpha (0.05) is split equally (alpha=0.025) between rMenB+OMV NZ objectives and MenABCWY objectives. Furthermore, within rMenB+OMV NZ, as well as within MenABCWY, objectives are tested hierarchically. If the first null hypothesis is rejected, then the testing will continue with the second hypothesis at same alpha. Same for 3rd, 4th, and so forth. Whenever a null hypothesis is not rejected, then the testing will stop.

As the comparator for MenABCWY non inferiority objective for the B component will be the selected schedule of rMenB+OMV NZ as determined in this study, the objectives of rMenB+OMV NZ will be analysed first. Additionally, if all null hypotheses related to rMenB+OMV NZ objectives will be rejected, the alpha (alpha=0.025) will be propagated to the MenABCWY part, and hypotheses related to MenABCWY objectives will be tested at full alpha (alpha=0.05). See Figure 2 for an explanation of the hierarchical testing (top to bottom, the order indicated by the arrows).

**Figure 2** Hierarchical testing of hypothesis

\* Alpha split equally between rMenB+OMV NZ and MenABCWY vaccine objectives.

If all rMenB+OMV NZ objectives achieved, MenABCWY vaccine objectives will be tested at full alpha.

\*\* If all objectives of rMenB+OMV NZ are met, the comparator will be the 0,2-months schedule. If the 0,2-months objective is not met, and the 0,6-months is met, then the 0,6-months schedule will be the comparator. If the 0,6-months is also not met, then the 0,2,6-months schedule will be the comparator.

Refer to Glossary of terms for definitions of test-based and responder-based vaccine effectiveness.

## 7. CONDUCT OF ANALYSES

### 7.1. Sequence of analyses

The final study report will contain at least the final analyses of all primary and secondary endpoints.

### 7.2. Statistical considerations for interim analyses

No interim analysis is planned for this study

## **8. CHANGES FROM PLANNED ANALYSES**

Not applicable

## **9. NON-STANDARD DATA DERIVATION RULES AND STATISTICAL METHODS**

The following sections describe additional derivation rules and statistical methods which are not presented in section 10.1.

### **9.1. Data derivation**

Not applicable

### **9.2. Statistical Method**

Not applicable

## **10. ANNEXES**

### **10.1. Business rules for standard data derivations and statistical methods**

This section contains GSK Vaccines' standard rules for data display and derivation for clinical and epidemiological studies.

#### **10.1.1. Attributing events to vaccine doses**

The dose relative to an event is the most recent study dose given to a subject prior to the start of a given event. For example, if the start date of an adverse event is between Dose 1 and Dose 2, the relative dose will be Dose 1.

If an event starts on the same day as a study dose, the relative dose will be derived from the additional information provided in the CRF using the contents of the flag indicating if the event occurred before or after vaccination. If 'after vaccination' is selected, the relative dose for the event will be the one administered on the start day of the event. If 'before vaccination' is selected, the relative dose for the event will be the dose prior to this one.

#### **10.1.2. Handling of missing data**

##### **10.1.2.1. Dates**

When partially completed dates (i.e. with missing day or month) are used in calculations, the following standard rules will be applied:

- A missing day will be replaced by 15
- A missing day and month will be replaced by June 30th.

The following exceptions apply:

- Adverse event start dates with missing day:
  - If the event starts in the same month as at least one of the study doses, the contents of AE.AESTRTPT (the flag indicating if the event occurred before or after vaccination) will be used to complete the date. If 'after vaccination' is selected, the imputed start date will match the first (or only) study dose given during that month. If 'before vaccination' is selected, the imputed date will be one day before the first (or only) study dose given during that month.
- Adverse event start dates with missing day and month:
  - If the event starts in the same year as at least one of the study doses, the contents of AE.AESTRTPT (the flag indicating if the event occurred before or after vaccination) will be used to complete the date. If 'after vaccination' is selected, the imputed start date will match the first (or only) study dose given during that

year. If 'before vaccination' is selected, the imputed date will be one day before the first (or only) study dose given during that year.

All other cases of incomplete AE or concomitant medication/vaccination start date will follow the standard rules above.

#### **10.1.2.2. Laboratory data**

Missing laboratory results (including immunological data) will not be replaced.

#### **10.1.2.3. Daily recording of solicited adverse events**

##### **10.1.2.3.1. Studies with electronic diaries**

For studies using electronic diaries for the collection of solicited adverse events, a solicited adverse events will be considered present only when a daily recording of grade 1 or more is present.

#### **10.1.2.4. Unsolicited adverse events**

Unsolicited adverse event summaries are including serious adverse events unless specified otherwise.

Missing severity, relationship with study vaccine, and outcome of unsolicited adverse events will not be replaced and will appear as 'UNKNOWN' in all statistical output.

#### **10.1.3. Data derivation**

##### **10.1.3.1. Age at vaccination in days**

When age at vaccination is to be displayed in days, it will be calculated as:

Age = date of vaccination minus date of birth

##### **10.1.3.2. Age at vaccination in months**

When age at vaccination is to be displayed in months, it will be calculated as the number of complete calendar months between the date of birth (DOB) and the date of vaccination. For example:

DOB = 10JUN2017, Date of vaccination = 09JUL2018 -> Age = 12 months

DOB = 10JUN2017, Date of vaccination = 10JUL2018 -> Age = 13 months

**10.1.3.3. Age at vaccination in years**

When age at vaccination is to be displayed in years, it will be calculated as the number of complete calendar years between the date of birth and the date of vaccination. For example:

DOB = 10SEP1983, Date of vaccination = 09SEP2018 -> Age = 34 years

DOB = 10SEP1983, Date of vaccination = 10SEP2018 -> Age = 35 years

**10.1.3.4. Weight**

Weight will be presented in kilograms. Weights reported in pounds will be converted as follows:

Weight in kilograms = Weight in pounds / 2.2

**10.1.3.5. Height**

Height will be presented in centimeters. Heights reported in feet and inches will be converted as follows:

Height in centimeters = Height in inches x 2.54

**10.1.3.6. Body mass index (BMI)**

BMI will be calculated as follows:

BMI = (Weight in kilograms) / (Height in meters)

**10.1.3.7. Temperature**

Temperatures will be presented in degrees Celsius (°C). Temperatures reported in degrees Fahrenheit (°F) will be converted as follows:

Temperature (Celsius) = ((Temperature (Fahrenheit) - 32) x 5)/9

### 10.1.3.8. Numerical serology results

Numerical serology results will be derived from the content of IS.ISORRES in the SDTM dataset. For assays with a specific cut-off, the following derivation rules apply:

IS.ISORRES	Derived value
“NEG”, “-”, or “(-)”	cut-off/2
“POS”, “+”, or “(+)”	cut-off
“< value” and value is <= assay cut-off	cut-off/2
“< value” and value is > assay cut-off	value
“> value” and value is < assay cut-off	cut-off/2
“> value” and value is >= assay cut-off	value
“value” and value is < cut-off	cut-off/2
“value” and value is >= cut-off	value
All other cases	missing

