### 10.1.3.8. Numerical serology results

Numerical serology results will be derived from the content of IS.ISORRES in the SDTM dataset. For assays with a specific cut-off, the following derivation rules apply:

IS.ISORRES	Derived value
“NEG”, “-”, or “(−)”	cut-off/2
“POS”, “+”, or “(+)”	cut-off
“< value” and value is <= assay cut-off	cut-off/2
“< value” and value is > assay cut-off	value
“> value” and value is < assay cut-off	cut-off/2
“> value” and value is >= assay cut-off	value
“value” and value is < cut-off	cut-off/2
“value” and value is >= cut-off	value
All other cases	missing

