### 10.1.3.9. Geometric mean titres (GMTs) and concentrations (GMCs)

Geometric Mean Titre (GMT) or Concentration (GMC) calculations are performed by taking the inverse logarithm of the mean of the log titre or concentration transformations. Antibody titres or concentrations below the cut-off of the assay will be given an arbitrary value of half the cut-off of the assay for the purpose of GMT/GMC calculation. The cut-off value is defined by the laboratory before the analysis and is described in the protocol.

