**5.3.1.7. Lot-to-lot consistency: MenABCWY - ACWY component**

Analysis set: The analysis of lot-to-lot consistency will be based on the PPS.

Statistical method: For each of the three ABCWY lots (Lots 1, 2 and 3 of the MenACWY component of the ABCWY vaccine), GMTs and 97.5% CIs will be calculated by exponentiating (base 10) the least squares means and the lower and upper limits of the 97.5% CIs of the log transformed titres (base10) obtained from an Analysis of Variance

(ANOVA) with factors for vaccine lot and randomization factors (i.e. region (US/ex-US), age category (10-17 YoA/18-25 YoA), previous MenACWY vaccination (y/n)).

Additionally, lot-to-lot GMT ratios will be computed for each pair of ABCWY lots.

Ninety-seven point five percent (97.5%) CIs for the ratios of GMTs will be constructed by exponentiating the difference of the least square means of the log transformed titres and the lower and upper limits of the 97.5% CIs on the difference obtained from the ANOVA model above.

**Lot-to-lot consistency criterion:** The three ABCWY lots will be considered equivalent if for each of the 4 serogroups A, C, W and Y and each pair of vaccine lots, the two-sided 97.5% CI on the ratio of GMTs at 1 month after the last vaccination will be contained within the interval [0.5, 2.0].

If the co-primary effectiveness objectives for rMenB+OMV NZ are met (Sections 5.3.1.1 through 5.3.1.6), then the above will be evaluated at 95% CI.

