**CONFIDENTIAL**

205416 [MENB REC 2ND GEN-038 (V72\_72)]

Statistical Analysis Plan Amendment 1

Objectives	Endpoints

Lot-to-lot consistency: MenABCWY vaccine
 
To demonstrate lot-to-lot consistency of the immune responses of 3 lots of the MenACWY component of the MenABCWY vaccine, as measured by hSBA GMTs directed against serogroups A, C, W and Y at 1 month after last vaccination (0,6-months).
 
Criterion:
 
The two-sided 97.5% CIsa for the ratio of hSBA GMTs of antibodies against serogroups A, C, W and Y are within the [0.5;2.0] equivalence interval for each pair of lots.
	
GMTs directed against serogroups A, C, W and Y for each lot (ABCWY-1 group, ABCWY-2 group, ABCWY-3 group) at 1 month after the last vaccination (Day 211, Month 7)

Immunological non-inferiority: MenABCWY vaccine vs. MenACWY vaccine
 
To demonstrate the immunological non-inferiority of the MenABCWY vaccine compared to the MenACWY vaccine as measured by the percentages of subjects achieving a 4-fold rise in hSBA titres against N. meningitidis serogroups A, C, W and Y at 1 month after the last MenABCWY vaccination (0,6-months) and 1 month after the MenACWY vaccination.
 
Criterion:
 
LL of the 2-sided 97.5% CIa for the group difference in percentages of subjects achieving a 4-fold rise* in hSBA titres is above -10%.
	
The percentages of subjects with 4-fold rise* in hSBA titres against N. meningitidis serogroups A, C, W and Y at 1 month after the:
 
 
last vaccination for the ABCWY group (pooled lots) (Day 211, Month 7), and
 
1 month after the MenACWY vaccination for the ACWY group (Day 31, Month 1) relative to baseline (Day 1, Month 0).
 

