**CONFIDENTIAL**

205416 [MENB REC 2ND GEN-038 (V72\_72)]  
 Statistical Analysis Plan Amendment 1

- Treatment allocation: At Day 1, prior to the study vaccination, subjects will be randomised to 1 of the 6 study groups according to a 5:5:3:3:3:1 ratio.
- Blinding: Observer-blind. Kindly refer to Protocol Section 7.3 for details on blinding and unblinding procedures.
- Sampling schedule:
  - A total of 4 blood samples\* will be collected from each subject at Day 1 (pre-vaccination blood sample; approximately 20 mL), at Day 31 (post-vaccination 1 blood sample; approximately 25 mL), at Day 91 (post-vaccination 2 blood sample; approximately 25 mL) and at Day 211 (post-vaccination-3 blood sample; approximately 25 mL).
  - Urine sampling: Urine samples for pregnancy testing will be collected from female subjects of child-bearing potential at Visit 1 (Day 1), Visit 3 (Day 61), Visit 5 (Day 181) and Visit 6 (Day 211) prior to the vaccination.

\* Insufficient blood volume may lead to test cancellation and jeopardise the statistical power. Hence, every effort must be done to collect blood volume as per protocol requirements.

- Data collection: standardised Electronic Case Report Form (eCRF). Solicited symptoms will be collected using a subject Diary (electronic Diary [eDiary]).
- Safety monitoring: Regular safety follow-up will be done through telephone calls (T). There will also be an extended safety follow-up (ESFU) phone call 12 months post-vaccination 3 (Day 181; Visit 5). This ESFU phone call will also mark the study conclusion. Refer to Protocol Table 3 and Protocol Section 8.5.3 for details on the safety follow-up.

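### Serology derivation rule (SAP 10.1.3.8) sets a 'greater than' result below the cut-off to half the cut-off, which the result does not support; 'greater than' results above the cut-off enter the lot-consistency ANOVA as exact titres with no sensitivity analysis

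*SAP*

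**What the plan says.** The derivation table in SAP 10.1.3.8 has two rows for results reported only as exceeding a value. The table is the same in Amendments 2 and 5, so this is current text.

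- Reported value below the cut-off, "> value” and value is < assay cut-off": the derived value is half the cut-off.
- Reported value at or above the cut-off, "> value” and value is >= assay cut-off": the derived value is the reported value itself.

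The same table ends with a row that sends all remaining cases to missing.

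Section 10.1.3.9 gives the reason for using half the cut-off: "Antibody titres or concentrations below the cut-off of the assay will be given an arbitrary value of half the cut-off of the assay". That covers titres that are below the cut-off. It does not cover titres whose position relative to the cut-off is unknown.

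The derived titres feed the primary lot-consistency objective. Section 2, Table 1 requires that the confidence intervals for the GMT ratios "are within the [0.5;2.0] equivalence interval for each pair of lots", for each of serogroups A, C, W and Y. Section 5.3.1.7 takes those ratios from an ordinary ANOVA on log10 titres with 97.5% intervals; if the rMenB+OMV NZ objectives are met, "then the above will be evaluated at 95% CI". Section 5.3.2.7 adds nothing to this analysis, and section 9 lists no study-specific derivation or method. The 5.3.x text is read from Amendment 4, because the Amendment 5 text of those sections is not in the part of the document at hand.

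**The concern.** The two rows raise different problems.

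The below-cut-off row is a logical error whenever it is used. A 'greater than' result whose bound lies under the cut-off leaves open on which side of the cut-off the titre falls. The rule decides that it is below and gives it a low number. A subject who is truly positive can then count as negative in a percentage above a threshold, and a low value enters the GMT.

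The at-or-above row ignores right-censoring. Substituting the upper limit can only understate a titre. The lot with the higher titres has more results cut off at the top, so its mean falls by more and the ratio between lots moves toward 1. The spread shrinks as well, which narrows the interval. In an equivalence test both effects favour passing. Lot consistency is a primary MenABCWY objective, so a prespecified rule that leans toward success needs at least a check.

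**Working it through.** **Inputs from the SAP.** 548 randomised per ABCWY lot and 25% dropout (section 3.3); equivalence limits 0.5 and 2.0; two-sided 97.5% interval (z = 2.241) or 95% interval (z = 1.960). The plan's evaluable number reproduces: 548 × 0.75 = 411 per lot.

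**Inputs the SAP does not give, so assumed.** SD of log10 titre (0.6, range 0.5 to 0.7), an upper limit L of the titration, and the share of results above it. The LOD and LLOQ values are redacted.

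**1. Below-cut-off row.** Let the cut-off be c and the result '> v' with v < c. The true titre exceeds v. If v ≥ c/2, the true titre is strictly greater than c/2, so the assigned number is impossible. Example with an assumed cut-off of 8: '>4' becomes 4. If v < c/2, the assigned number is possible but has no support.

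The effect on a lot's log10 mean is the share of such results times the distance from that mean down to c/2. Assume a true ratio of 1.80 (log10 = 0.255) and c/2 lying 1.5 log10 below the lower lot's mean.

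- 5% of such results in the lower lot only: 0.255 + 0.05 × 1.5 = 0.330, so the ratio becomes 2.14 (away from 1).
- 5% in the higher lot only: 0.255 − 0.05 × (1.5 + 0.255) = 0.167, so the ratio becomes 1.47 (toward 1).

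With SD 0.6, the chance of passing the 97.5% interval goes from 12.6% to 0.2% in the first case and to 75.7% in the second. The direction therefore depends on where such results fall.

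**2. At-or-above row.** Take two lots with normal log10 titres, means 0 and log10 2 = 0.301, common SD σ, and L set so that a chosen share of the lower lot exceeds it. With a = (L − μ)/σ, the mean after substitution is

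μΦ(a) − σφ(a) + L(1 − Φ(a)).

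The SDs after substitution, s0 and s1, follow from the matching second moment. Then SE = √((s0² + s1²)/411), and the chance of passing at the 2.0 limit is Φ((0.301 − difference)/SE − z).

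Worked case, σ = 0.6, 5% of the lower lot censored:

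- L = 1.645 × 0.6 = 0.987. For the higher lot a = (0.987 − 0.301)/0.6 = 1.143, so 12.6% of it is censored.
- The means become −0.0125 and 0.2632. The difference is 0.2758 before rounding, a ratio of 1.887.
- The SDs become 0.574 and 0.536. SE = √((0.3295 + 0.2873)/411) = 0.0387.
- (0.3010 − 0.2758)/0.0387 = 0.652. For the 97.5% interval, Φ(0.652 − 2.241) = 5.6%. For the 95% interval, Φ(0.652 − 1.960) = 9.5%.

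| Lower lot censored | Higher lot censored | Expected ratio | Pass, 97.5% CI |
|---|---|---|---|
| 0% | 0% | 2.00 | 1.25% |
| 1% | 3.4% | 1.97 | 1.8% |
| 5% | 12.6% | 1.89 | 5.6% |

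Over SD 0.5 to 0.7 and 2% to 10% of the lower lot censored, the pass chance runs from 2.1% to 29%. The top of that range needs about 25% of the higher lot off-scale.

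If the share is counted over both lots together, the figures for SD 0.6 are 1.5% at 1%, 2.9% at 5% and 6.8% at 10%. The two scales agree: 5% of the lower lot is (5 + 12.6)/2 = 8.8% overall.

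**3. From one interval to the criterion.** Three lot pairs by four serogroups give 12 intervals, all of which must pass. The joint pass probability cannot exceed that of any one interval. The figures above are therefore ceilings for the case in which that one pair truly differs by a factor of 2.

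**The case against.** The strongest reply is that nothing in the document shows that these results will occur. The table is introduced in 10.1 as the sponsor's standard rules across studies, so its rows are not evidence about this assay. The SAP gives no upper titration limit, no expected share and no SD, and does not say whether high sera are diluted further to an end point. If they are, or if about 1% or fewer of results are affected, the effect on lot consistency is negligible. This stands, and it makes the second part of the point conditional. It does not rescue the below-cut-off row, which gives an unsupported value each time it is applied.

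A reader might infer that both rows shrink lot ratios and that the lot-consistency test is therefore too easy to pass. The document does not support that. Only the at-or-above row shrinks ratios. The below-cut-off row can move them either way and can make the test harder, as the 2.14 case shows. Even for the at-or-above row the size rests wholly on an unknown share, and it concerns one of 12 intervals.

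It is also fair to say that no effect is shown on the responder-based endpoint, which counts strains killed in the enc-hSBA. For the four-fold rise, section 5.3.1.8 uses LOD and LLOQ multiples when baseline is below the LLOQ, so the substituted number is not itself the multiplier there. Neither endpoint is claimed as affected by a stated amount.

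Finally, replacing the primary ANOVA would go further than the evidence warrants.

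**Conclusion.** The below-cut-off row is wrong as written and should be changed. It treats an undetermined result as negative and, when the reported value is at least half the cut-off, assigns a titre the result excludes. Its frequency is unknown, and its effect on GMTs can go either way.

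The at-or-above row leaves right-censoring unaddressed in a primary equivalence test. The resulting bias is possible, not established. For a pair truly at the 2.0 limit, with 411 per lot and an assumed SD of 0.6, one 97.5% interval passes with probability 1.8% (1% of the lower lot censored) or 5.6% (5% censored), against a nominal 1.25%. With no such results there is no effect. These are not rates at which the whole lot-consistency criterion would be falsely met.

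**What to change.** - In 10.1.3.8, change the derived value for a 'greater than' result below the cut-off from half the cut-off to missing (not evaluable), for GMTs and for any threshold above the reported value. For a threshold at or below the reported value the result remains informative.
- Keep the ANOVA in 5.3.1.7 as primary. In 5.3.2.7, prespecify a sensitivity analysis that treats 'greater than' results as right-censored at the reported value, using normal regression on log10 titre with the same factors (for example PROC LIFEREG). With nothing censored it returns the same GMT ratios as the ANOVA.
- Report the number of 'greater than' results per lot and serogroup, so that a reader can see whether the issue arises.

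Cost: SAP wording, one additional model run and one small table. No new data or assays are needed.

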### 10.1.3.9. Geometric mean titres (GMTs) and concentrations (GMCs)

Geometric Mean Titre (GMT) or Concentration (GMC) calculations are performed by taking the inverse logarithm of the mean of the log titre or concentration transformations. Antibody titres or concentrations below the cut-off of the assay will be given an arbitrary value of half the cut-off of the assay for the purpose of GMT/GMC calculation. The cut-off value is defined by the laboratory before the analysis and is described in the protocol.

### 10.1.3.10. Onset day

The onset day for an event (e.g. AE, medication, vaccination) is the number of days between the last study vaccination and the start date of the event. This is 1 for an event occurring on the same day as a vaccination (and reported as starting after vaccination).

### 10.1.3.11. Duration of events

The duration of an event with a start and end date will be the number of days between the start and end dates plus one day, i.e. an event that starts on 03MAR2018 and ends on 12MAR2018 has a duration of 10 days.

### 10.1.3.12. Counting rules for combining solicited and unsolicited adverse events

For output combining solicited and unsolicited adverse events, all serious adverse events will be considered general events since the administration site flag is not included in the expedited adverse event CRF pages.

Multiple events with the same preferred term which start on the same day are counted as only one occurrence.

